## INTRODUCTION

During many surgeries, increased muscle tension makes it harder for the surgeon to expose the site of surgery and work within the incision. Neuromuscular blockade (NMB) drugs such as Vecuronium bind to neurotransmitter (acetyl choline) receptors at the neuromuscular junction, blocking their action and producing muscle relaxation. This muscle relaxation allows easier retraction of muscle tissues and manipulation of structures in the wound. Improved surgical conditions are likely to result in improved patient outcomes. While increased depths of NMB have been shown to optimize surgical conditions during intra-abdominal and retroperitoneal procedures, the impact of NMB depth has not been reported for orthopedic surgeries. To address this, we propose to study the effect of NMB depth on surgical conditions during total hip replacement (THR).

## BACKGROUND

THR is a very common surgical procedure in the US and approximately 600 cases are performed per year at MMC. The hip joint is a ball and socket joint, the head of the femur is the ball and the cup of the pelvic bone is the socket. THR requires an incision through skin and muscle with retraction of the incised muscles to expose the head of the femur which is then removed. The femoral prosthesis is inserted into the femur and next the ball of the femoral prosthesis is then inserted (reduced) into the socket. Thus, tension in the muscles can interfere with their retraction during exposure or with extracting or reducing the femoral head and patients with more developed musculature (males, younger age, physically active) could potentially present a greater challenge to the surgeon.

At MMC general anesthesia utilizing neuromuscular blockade is the routine anesthetic technique. The primary goal of NMB during THR is to facilitate retraction of muscles around the site of surgery to increase the surgeon's view of the operative site during the operation without the need for a longer incision, and to facilitate reinsertion (reduction) of the prosthesis at the end of surgery. Newer minimally invasive hip replacement techniques which use smaller incisions may theoretically require even greater depth of NMB to produce optimal surgical conditions.

Until recently, the depth of NMB during surgery has been limited in practice by the time it takes to reverse the effects and allow adequate return of neuromuscular function for

safe extubation and spontaneous ventilation. The effects of NMB wear off with time; however, this process can be prolonged and in most cases NMB is reversed using medication. Older reversal medications such as Neostigmine act by increasing levels of acetylcholine at the neuromuscular junction, where it competes with the NMB agent for receptor sites. There is however a ceiling effect with this method, which limits rapid reversal of deeper NMB, especially when that deeper NMB is needed near the end of a surgery such as in THR. Thus, the constraints of reversal time limit the depth of NMB that is practical during surgery.

The FDA, however, recently approved Sugammadex for use in the US and was approved for routine use at MMC by the Pharmacy and Therapeutics Committee in May of 2016 (see appendix). In their meeting minutes, the P&T Committee noted that “in clinical trials, Sugammadex produced significantly faster reversal times for both moderate and deep blockade compared to the combination of neostigmine and glycopyrrolate. Reversal times were usually less than 5 minutes.” The P&T Committee reviewed recent literature and studies, as Sugammadex has been thoroughly reviewed for patient safety and concluded that hypersensitivity reactions are mild or moderate and there is a low incidence of anaphylaxis. Sugammadex is a new NMB reversal agent which acts by sequestering rather than competing with the NMB drugs and thus has no ceiling effect, allowing timely and effective reversal of both moderate and deep degrees of NMB. While new to the US market, this drug has been used widely and safely around the world since 2007, and has been in routine clinical use as a reversal agent at MMC since approval without incident. Sugammadex allows the anesthesiologist to maintain a deeper degree of NMB throughout THR without causing undue delay at the end of the operation. We estimate that its use reduces time to reversal from a deep block by 10 to 20 minutes.

We hypothesize that a deeper degree of NMB during THR will improve surgical conditions for the surgeon and may reduce surgical time. To explore this, we propose to perform a randomized controlled trial that will compare the effect of deep NMB versus moderate NMB, on surgical conditions during THR.

#### SPECIFIC AIMS

- 1) Assess difference in surgical conditions between moderate and deep NMB groups.  
Enrolled patients will be randomized to receive moderate (n=58) or deep (n=58) NMB. Difference in surgical conditions will be evaluated by:
  - a) The number of requests from the surgeon for additional relaxation (NMB) during the procedure. At any time during the operation if the surgeon feels the muscle tension is interfering with ease of operation he will ask for additional muscle relaxation. If the patient is moderately relaxed they will be converted to deep relaxation with additional muscle relaxants. If they are already deeply relaxed no additional relaxants will be administered (as is our current practice). All requests will be recorded.
  - b) Rating by the surgeon after each surgery using an internally developed satisfaction scale. The scale was developed by modifying a scale used in a previous study of muscle relaxation in intra-abdominal surgery to specify two key elements identified by our surgeon: ease of muscle retraction and femur manipulation.

- 2) Assess the impact of deep vs moderate NMB on time of surgery, measured from the time of incision to joint reduction.

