## SIGNIFICANCE

If we identify improved surgical conditions with deeper relaxation we will incorporate deep NMB into our routine anesthesia practice for THR.

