#### *Sample size*

Sample size calculations, performed using NQuery software (Statistical Solutions Ltd, Boston, MA), were based on a chi square test, comparing the current frequency among surgeries of surgeon requests for additional NMB (estimate, 50%) and an anticipated effect size of 50% (absolute frequency of 25% for requests for additional NMB in the deep NMB group). A sample size of  $n=58/\text{group}$  ( $n=116$  total) would give 80% power to detect this difference at alpha = 0.05. Assuming incomplete data and cancelled surgeries among 10% of patients, we will enroll a total of 128 (64/group). [name] performs ~400 THR surgeries per year at MMC, of which ~280 are among patients aged 50-70 years; thus a minimum enrollment rate of 46% would be required to achieve this sample size over a one year period.

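### Aim 1 judges surgical conditions by two outcomes with no primary named, and the commitment to adopt deep NMB does not say which one decides

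*Combined protocol and SAP*

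**What the plan says.** In the combined protocol and SAP, Aim 1 of the Specific Aims opens with "Difference in surgical conditions will be evaluated by" and lists two measures side by side: (a) the surgeon's requests for additional relaxation and (b) the surgeon's rating after each operation. Neither is called primary, and no order or joint rule is given. Time from incision to joint reduction is a separate Aim 2.

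The Significance section then makes a commitment: "If we identify improved surgical conditions with deeper relaxation we will incorporate deep NMB into our routine anesthesia practice for THR". It does not say whether requests, the rating, or both must show the improvement.

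The Sample size section uses requests only. The assumed rate is 50% in current practice against an "absolute frequency of 25% for requests for additional NMB in the deep NMB group". It states that 58 per group "would give 80% power to detect this difference at alpha = 0.05". This is the only alpha in the document.

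Data Analysis compares categorical outcomes by chi-square and continuous outcomes by t test or a nonparametric equivalent, by intention to treat first. It gives no hierarchy, no multiplicity adjustment and no alpha for the rating.

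**The concern.** The plan ties a change of routine practice to a construct, surgical conditions, that it measures in two ways, and it gives no rule for combining them. If the two measures agree, nothing is lost. If they disagree, someone must decide after seeing the results which one counts, and the 5% error rate used for sizing no longer describes the conclusion.

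A split is realistic. Under Specific Aims and NMB administration, a moderate-group patient whose surgeon asks for more relaxation is taken to deep block. Under Data Collection, the overall grade is given after the operation. If depth matters, requests could differ between groups while the grades are drawn together.

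**Working it through.** **Inputs from the document.** Request rates 50% and 25%, 80% power, alpha 0.05 and 58 per group (Sample size); two measures of surgical conditions (Specific Aims, Aim 1); separate unadjusted tests (Data Analysis).

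**Assumptions, not in the document.** Each measure is tested at two-sided 0.05. Either one suffices for adoption. The correlation ρ between the two test statistics lies between 0 and 0.9, with signs set so that positive favours deep NMB.

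**Step 1: reproduce the plan's sample size.** For a two-sided chi-square test with pooled variance and no continuity correction, the mean rate is (0.50 + 0.25)/2 = 0.375 and

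n = [1.960·√(2·0.375·0.625) + 0.842·√(0.50·0.50 + 0.25·0.75)]² / 0.25²

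= [1.960·0.6847 + 0.842·0.6614]² / 0.0625 = 57.7, rounded up to 58 per group.

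This matches the plan. Power at 58 is 80.2%. A one-sided test would need 46 and a continuity-corrected test 66, so the sizing was two-sided and uncorrected. The benchmark for one outcome is therefore 5% for any difference, and 2.5% for a difference favouring deep NMB.

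**Step 2: error rate if either measure suffices.** With no true effect, and (Z1, Z2) bivariate standard normal with correlation ρ:

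- any difference declared: 1 − P(|Z1| ≤ 1.96 and |Z2| ≤ 1.96)
- false adoption (deep NMB favoured): 1 − P(Z1 ≤ 1.96 and Z2 ≤ 1.96)

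At ρ = 0 these are 1 − 0.95² = 9.75% and 1 − 0.975² = 4.94%.

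| ρ (assumed) | Any difference, two-sided | False adoption |
|---|---|---|
| 0 | 9.75% | 4.94% |
| 0.5 | 9.07% | 4.54% |
| 0.7 | 8.35% | 4.17% |
| 0.8 | 7.81% | 3.90% |
| 0.9 | 7.04% | 3.52% |
| One outcome only | 5% | 2.5% |

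False adoption is 3.52/2.5 = 1.4 to 4.94/2.5 = 2.0 times the single-outcome rate.

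**Step 3: check with discrete data.** A null simulation used 20,000 runs, 58 per group, a 50% request rate, an assumed five-category rating, an uncorrected chi-square test and a rank test. The any-difference rate was 9.8% with unrelated outcomes. It was 7.7% when both came from nearly the same latent variable (test-statistic correlation about 0.84 in size). False adoption ran from 5.2% to 3.9%. The normal approximation is adequate.

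**Step 4: what each remedy costs.** Naming requests as primary, or testing in a fixed order, keeps the error at 5% two-sided with 58 per group. Splitting alpha as 0.025 + 0.025 also controls it, but power for requests at 58 falls to 71.2%. Restoring 80% would take 70 per group, or 70/0.9 = 77.8, so 78, after 10% loss.

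**The case against.** The strongest reply is that no either-outcome rule is written down. The Significance section is one sentence of intent, not a decision rule with a threshold. Aim 1 can equally be read as requiring both measures or weighing them together. If both had to be significant, the two-sided error would be at most 5%. Requests are listed first and are the only outcome sized, which suggests an intended primary. All of this stands, so the figures are conditional. It does not settle the matter, because the plan never says which reading applies.

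Two further limits also stand. The 0.05 for the rating is inferred from the only alpha given. The correlation is unknown and may be high, since one surgeon supplies both measures in the same operation. That is why the range extends to 0.9; at 0.95 the any-difference figure is 6.5%.

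A reader might infer three stronger things that the documents do not support:

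- **That false adoption runs at 8-10%.** Adoption follows only from a result favouring deep NMB, so its like-for-like change is from 2.5% to about 3.5-4.9%. The larger figures describe declaring a difference in either direction.
- **That surgical time is a third route to adoption.** The Significance section refers to surgical conditions, and time sits in a separate aim.
- **That conversion of moderate patients inflates the type I error.** If depth has no effect, conversion changes nothing. It makes split results more likely only when depth does have an effect.

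**Conclusion.** The concern holds as a gap in the decision rule: two measures of equal standing, a commitment to change practice, no primary outcome, and no verdict for a split result. It should be closed before the data are analysed.

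The numerical inflation is moderate and rests on the three assumptions in the working: either measure suffices, each is tested at two-sided 0.05, and the correlation is 0 to 0.9. Under them, false adoption is 1.4 to 2.0 times the single-outcome rate. The sample size calculation is sound for requests and is not in question.

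**What to change.** In the Significance and Data Analysis sections, state the following:

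- The primary outcome is the comparison that was sized: the proportion of surgeries with at least one request, by intention to treat, chi-square, two-sided 0.05. The adoption conclusion rests on it. Aim 1(a) speaks of the number of requests, so its wording should be aligned with this.
- The surgeon's rating is the key secondary outcome, tested at two-sided 0.05 only if the primary is significant. Otherwise it is reported with a 95% confidence interval as supportive information.
- Incision-to-reduction time remains a secondary outcome under Aim 2 and does not drive adoption.

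This takes a few sentences and no extra patients; 58 per group and 80.2% power for requests are unchanged. The real cost is that a significant rating alone no longer supports adoption. With 80.2% power, the primary would miss about 20% of the time (1 − 0.802 = 0.198) even if the planned effect were true, and a favourable rating could not rescue it. If the investigators want the rating to carry weight on its own, the alpha split in the working is the alternative, at the loss of power or larger sample shown there.

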## SIGNIFICANCE

If we identify improved surgical conditions with deeper relaxation we will incorporate deep NMB into our routine anesthesia practice for THR.

## METHODS

### Human subjects

#### *Eligibility*

Male and female patients between 50 and 75 years old who are scheduled at MMC for elective THR by a single surgeon ([name]) will be potentially eligible to participate in the study.

Inclusion Criteria include: ASA physical status 1-3 (the American Society of Anesthesiologists standard preoperative risk stratification assignment – add ref), age 50-75 years old, English speaking, able to provide informed consent, BMI equal to or less than  $30 \text{ kg/m}^2$ , non-emergent THR by anterolateral minimally invasive non-cemented total hip arthroplasty (ALTHA).

Exclusion criteria include: revision surgery, bilateral THR, ASA 4+, below 50 or over 75 years old, unable to provide consent, BMI greater than  $30 \text{ kg/m}^2$ , women taking oral contraceptives as Sugammadex interferes with their efficacy, contraindications to general inhalation anesthesia, such as malignant hyperthermia, or contraindications to NMB such as known allergy to NMB, and chronic kidney disease.

#### *Sample size*

Sample size calculations, performed using NQuery software (Statistical Solutions Ltd, Boston, MA), were based on a chi square test, comparing the current frequency among surgeries of surgeon requests for additional NMB (estimate, 50%) and an anticipated effect size of 50% (absolute frequency of 25% for requests for additional NMB in the deep NMB group). A sample size of  $n=58/\text{group}$  ( $n=116$  total) would give 80% power to detect this difference at alpha = 0.05. Assuming incomplete data and cancelled surgeries among 10% of patients, we will enroll a total of 128 (64/group). [name] performs ~400 THR surgeries per year at MMC, of which ~280 are among patients aged 50-70 years; thus a minimum enrollment rate of 46% would be required to achieve this sample size over a one year period.

#### *Recruitment/Enrollment*

Scheduled patients will be screened for potential eligibility by surgery office staff and the study will be introduced to identified patients during their pre-operative appointment with the surgeon ([name]). Any patient who would like to hear more about the study will be contacted by the research coordinator for follow up. The research coordinator will provide additional information about the study and mail a copy of the informed consent form for patients to review. On the day of surgery their

anesthesiologist will elicit and answer any questions or concerns and patients who decide to enroll in the study will give informed consent at that time.

#### *Randomization*

Patients will be randomized to moderate (Group 1) or deep (Group 2) NMB using a permuted block design (blocks of n=4 and n=6) that is stratified by patient sex. The randomization plan will be developed using NQuery software (Statistical Solutions Ltd, Boston, MA). Sequentially numbered group assignments will be placed in opaque envelopes, with a separate series of envelopes for male and female patients. Immediately before each surgery, the Research Coordinator will retrieve manually the next envelope in sequence from the male or female series, as appropriate, and give this to the anesthesiologist. The surgeon will be blinded to group assignment.

#### Anesthesia procedures

##### *NMB monitoring*

Depth of NMB is routinely monitored during surgery using a device that applies a transcutaneous electrical stimulus over the target nerve using while the muscular contraction is observed in the target muscle group. In most surgeries the ulnar nerve is stimulated which causes contraction of the adductor pollicis longus which produces movement of the thumb. It is the movement of the thumb which is recorded. There are two modes of stimulation used to quantify depth of NMB. The first mode, train of four (TOF) measures the respective muscle contractions to nerve stimulation of four successive stimuli and is reported as the number of muscle contractions observed, for example 2 out of four contractions. The second, post tetanic count (PTC) reports the number of responses to four stimuli after a sustained (tetanic) stimulus. PTC is used when NMB completely blocks the muscular contractions to all four stimuli in the TOF. In this study we will use the TOF Watch device to stimulate and measure the neuromuscular response quantitatively. This device is in routine clinical use at the MMC.

##### *NMB administration*

Vecuronium will be used as NMB drug in all study patients; this agent is currently used in over 90% of THR cases at MMC. As is currently routine Vecuronium will be given after initiation of general anesthesia with propofol to facilitate intubation and further doses of Vecuronium will be given throughout the case as noted below to maintain NMB at the desired depth until the femoral implant is reduced. After the intubating dose of Vecuronium, NMB depth will be monitored every 5 minutes and dosing will be adjusted as needed to maintain a constant depth of NMB according to our current routine practice.

Group 1: Moderate NMB: Intubating dose of Vecuronium of 0.1 mg/kg (IBW) and re-dosing with 0.0125 to 0.05 mg/kg as needed to achieve and maintain 1 to 2 TOF contractions. Redosing in this manner is a current clinical practice.

Group 2: Deep NMB: Intubating dose of Vecuronium of 0.2 mg/kg (IBW) and re-dosing with 0.025 to 0.1 mg/kg to achieve and maintain zero twitches in the TOF, and post tetanic count (PTC) of 1 to 2 contractions. This level of blockade is new to the practice since approval of the drug for use at MMC but is in common use since the advent of Sugammadex.

The surgeon may request additional relaxation at anytime for inadequate surgical conditions thought to be related to muscle tension. All requests will be recorded. Patients in the moderate NMB group will receive additional doses of vecuronium to achieve deep NMB (PTC of 1- 2). In the deep NMB group with PTC of 1-2, a saline dose without NMB will be given.

#### *NMB reversal*

Sugammadex will be given for reversal of NMB after the prosthesis has been reduced, using routine dosing of 2 mg/kg for the moderate group and 4 mg/kg for the deep group, per package insert by Merck (attached).

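### The sugammadex dose is fixed by group, so a moderate-group patient converted to deep block and still deep at reversal would, on a literal reading, get half the dose the protocol pairs with that depth

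*Combined protocol and SAP*

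**What the plan says.** The NMB reversal section sets both the time and the dose of sugammadex. On time: "Sugammadex will be given for reversal of NMB after the prosthesis has been reduced". On dose: "using routine dosing of 2 mg/kg for the moderate group and 4 mg/kg for the deep group, per package insert by Merck (attached".

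The NMB administration section gives the two groups different depth targets. The moderate group is kept at 1 to 2 train-of-four (TOF) contractions. The deep group is kept at zero TOF twitches with a PTC of 1 to 2. Vecuronium is given to "maintain NMB at the desired depth until the femoral implant is reduced", and "NMB depth will be monitored every 5 minutes".

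Both the Specific Aims and the NMB administration section say what happens when the surgeon asks for more relaxation in a moderate-group patient. The aims state: "If the patient is moderately relaxed they will be converted to deep relaxation with additional muscle relaxants". The administration section states: "Patients in the moderate NMB group will receive additional doses of vecuronium to achieve deep NMB", and defines that depth as PTC 1 to 2. Deep-group patients already at that depth receive saline instead.

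**The concern.** After conversion, a moderate-group patient has been taken to the depth that defines the deep group, but the reversal rule refers only to the group. The text supplied neither assigns a reversal dose to converted patients nor says that the dose follows the depth measured at reversal.

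What is at stake is patient safety. The Background section describes the limit on block depth as "the time it takes to reverse the effects and allow adequate return of neuromuscular function", and ties this to safe extubation and spontaneous breathing. The protocol itself pairs the deeper block with twice the dose. Too small a dose could leave a patient incompletely reversed.

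The effect on the trial data is narrow. It would reach only the recovery items under Data Collection: time to extubation, additional reversal medication, intubation, ventilation and desaturation. Requests for relaxation, the surgeon's rating and incision-to-reduction time do not depend on the reversal dose.

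**Working it through.** **The plan's own figure.** The Sample size section is the source of the request rate: "comparing the current frequency among surgeries of surgeon requests for additional NMB (estimate, 50" percent. It sets this against 25% in the deep group, with 80% power and alpha 0.05. Sidedness is not stated; two-sided is assumed. With a pooled-variance chi-square test and no continuity correction:

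- n = [1.960 × √(2 × 0.375 × 0.625) + 0.842 × √(0.50 × 0.50 + 0.25 × 0.75)]² / (0.50 − 0.25)²
- n = (1.342 + 0.557)² / 0.0625 ≈ 57.7, rounded up to 58 per group

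The stated 58 per group is reproduced, with power 80.2%. The concern does not depend on this figure; it supplies the group size and the request rate used below.

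**Dose by group and by depth.**

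| Patient | Target depth | Dose as written |
|---|---|---|
| Moderate group, no request | TOF 1 to 2 | 2 mg/kg |
| Moderate group, after a request | PTC 1 to 2 | 2 mg/kg (literal reading) |
| Deep group | TOF 0, PTC 1 to 2 | 4 mg/kg |

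The second and third rows share a depth but not a dose. The ratio is 2/4 = 50%.

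**Can a converted patient still be deep at reversal?** Reduction of the implant ends maintenance of the block, and it is also the point after which sugammadex may be given. No interval for the block to lighten is stated. Requests may come at any time, and the Background section names reduction of the prosthesis as one purpose of the block, so a request shortly before reversal is foreseeable.

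**How many are converted?** Expected number = 58 × request rate, with the 2.5th to 97.5th percentiles of the binomial distribution:

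| Request rate in moderate group | Expected conversions of 58 | Binomial 95% range |
|---|---|---|
| 50% (plan) | 29 | 22 to 36 |
| 40% (assumed) | 23.2 | 16 to 31 |
| 30% (assumed) | 17.4 | 11 to 24 |

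**How many of those are still deep?** Let s be the share of converted patients at PTC 1 to 2 when reversal is given. At the plan's rate the number affected is 29 × s, and the documents do not give s.

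- If the depth to be maintained after conversion is deep block, all 29 could be at PTC 1 to 2 at reduction (s up to 1).
- If it is still the moderate target of TOF 1 to 2, only patients converted too late to lighten are affected (s anywhere from 0 to 1).

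The range is therefore 0 to 29 of 58.

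**The case against.** The strongest objection is that the dosing sentence does not stop at the two doses. It calls them routine and refers to a package insert that is attached to the protocol but was not supplied for review. If the insert sets the dose by depth of block, converted patients may be covered by reference. The anesthesiologist also knows the assignment, checks depth every 5 minutes with a quantitative device, and is not barred from giving more: additional reversal medication is one of the items tracked. It can be added that anyone who accepts that 4 mg/kg goes with PTC 1 to 2 could infer the converted patient's dose in the same way. Finally, reversal after reduction sets only an earliest time, and 29 counts conversions, not under-dosed patients.

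Much of this stands. It is quite possible that clinicians would dose by depth, no under-dosing has been shown, and the number affected could be zero.

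What does not stand is the view that the text already settles the matter. The protocol uses group to mean randomised group: the Randomization section defines it so, and the NMB administration section keeps the moderate label while deepening the block. Data Analysis separates the depth assigned from the depth received, so the mismatch was foreseen for analysis but not for reversal. The safeguards work only if the clinician departs from the group rule as written. Tracking extra reversal and desaturation detects a problem after it has occurred.

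**Conclusion.** The concern holds. As written, the rule gives a converted patient who is still at PTC 1 to 2 at reversal 2 mg/kg, 50% of the dose the protocol pairs with that depth. At the plan's request rate, 29 of 58 moderate-group patients are expected to be converted, and between 0 and 29 could still be deep at reversal.

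This rests on three assumptions: that group means randomised group; that the plan's 50%, which describes current surgeries, applies to the moderate arm; and that the unseen insert does not override the stated doses. The documents give no data on how 2 mg/kg performs at PTC 1 to 2, so the clinical risk per patient cannot be sized.

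The point should be fixed because it concerns safety and the correction is simple. It is not a threat to the specific aims or the sample size.

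**What to change.** Amend the NMB reversal section so that the dose follows the last TOF or PTC reading before reversal, whatever the randomised arm: 2 mg/kg at 1 to 2 TOF contractions; 4 mg/kg at TOF 0 with PTC 1 to 2; any other reading according to the attached package insert. Record that reading, if the data collection sheet (attached to the protocol, not supplied for review) does not already do so.

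The cost is one protocol sentence and possibly one data field. Both doses and the monitoring are already in the protocol. The one small downside is that the moderate arm will contain both reversal doses; total sugammadex dose is already collected, so this can be described in the results.
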